4.5 Follow-up of subjects withdrawn from treatment

Since there is no intervention involved in the study, there is no need for follow up of withdrawn participants.

4.6 Premature termination of the study

There are no expected reasons for premature termination of the study.

5. SAFETY REPORTING

All safety reporting will be handled in accordance with METC protocol

5.1 Temporary halt for reasons of subject safety

In accordance to section 10, subsection 4, of the WMO, the sponsor will suspend the study if there is sufficient ground that continuation of the study will jeopardise subject health or safety. The sponsor will notify the accredited METC without undue delay of a temporary halt including the reason for such an action. The study will be suspended pending a further positive decision by the accredited METC. The investigator will take care that all subjects are kept informed.

5.2 AEs, SAEs and SUSARs

5.2.1 Adverse events (AEs)

Adverse events are defined as any undesirable experience occurring to a subject during the study, whether or not considered related to [the investigational product / the experimental intervention]. All adverse events reported spontaneously by the subject or observed by the investigator or his staff will be recorded.

5.2.2 Serious adverse events (SAEs)

A serious adverse event is any untoward medical occurrence or effect that at any dose:

- results in death;
- is life threatening (at the time of the event);
- requires hospitalisation or prolongation of existing inpatients' hospitalisation;
- results in persistent or significant disability or incapacity;
- is a congenital anomaly or birth defect;
- Any other important medical event that may not result in death, be life threatening, or require hospitalization, may be considered a serious adverse experience when, based upon appropriate medical judgement, the event may jeopardize the subject or may require an intervention to prevent one of the outcomes listed above.

The sponsor will report the SAEs through the web portal *ToetsingOnline* to the accredited METC that approved the protocol, within 15 days after the sponsor has first knowledge of the serious adverse events.

SAEs that result in death or are life threatening should be reported expedited. The expedited reporting will occur not later than 7 days after the responsible investigator has first knowledge of the adverse event. This is for a preliminary report with another 8 days for completion of the report.

5.3 Follow-up of adverse events

All AEs will be followed until they have abated, or until a stable situation has been reached. Depending on the event, follow up may require additional tests or medical procedures as indicated, and/or referral to the general physician or a medical specialist. SAEs need to be reported till end of study within the Netherlands, as defined in the protocol

6. STATISTICAL ANALYSIS

Part I – Comparison of the ESM to SR-BDs and other retrospective questionnaires

In case of incomplete ESM data, we will not use imputation techniques as these techniques have similar assumptions on the mechanisms of missing data as the statistical model described in the remaining text.

Experience Sampling Methods produce complex multilevel data structures, and analysis techniques need to take the variation between subjects and repeated measures within subjects into account. Associations between urological symptom scores of the SR-BD and corresponding ESM scores will be tested using linear mixed-effects models, with a random intercept to account for clustering of measurements within patients, and an autoregressive (AR1) covariate structure to account for correlations of measurements over time. Currently the SR-BD can be seen as the standard method and will therefore be used as dependent variable in the analysis. For each participant, ESM day-mean scores of individual symptoms will be used as predictor, to test whether average symptom scores of the day reflect the day-mean SR-BD scores.

To quantify the difference of scores between the two methods, ESM data will be subtracted from corresponding day-mean SR-BD scores, resulting in a delta score, which will be statistically tested using the same multilevel analysis, adjusting for repeated measures. In like manner, the differences between the mean SR-BD scores and ESM maximum scores of the day will be tested.

To investigate if certain patient characteristics lead to a different retrospective perception of urgency, possible predictors of a larger delta-score (i.e. the differences in urgency reporting between ESM day-mean scores and the day-mean SR-BD scores) will be tested: i.e. gender, age, presence of comorbid panic disorder and psychological symptoms (HADS).

Part II Validation

The COSMIN guidelines are used to validate the Experience Sampling Method as a healthrelated ePRO. In this COSMIN (COnsensus-based Standards for selection of health Measurement INstruments) checklist manual, the methodology to examine responsiveness, i.e. "the instruments ability to detect change over time in the construct to be measured" gives the following instructions.⁵⁹⁻⁶¹ Studies evaluating the measurement properties of an instrument should be of high methodological quality to guarantee appropriate conclusions about the measurement properties of the instrument. Therefore, the COSMIN initiative developed a taxonomy of measurement properties relevant for evaluating health instruments, with three domains: reliability, validity and responsiveness. Each domain contains one or more measurement property:⁵⁹

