3.4 Sample size calculation

The outcome of the ESM is multidimensional; it gives information about the (urological) complaints but also the context in which the complaints arise. An inter-individual analysis can be made with the use of ESM, and because of this extensive data can be collected per patient.

An appropriate sample size can therefore not be made.

In previous literature the sample size differs from N=5 ²⁷, N= 10 ³⁸, N = 19 ³⁹, N= 26 ¹ to N=40 ⁴⁰. In the study of Cabrita et. al. random slopes could not be included in the multilevel regression analysis because of the sample size being too small to validly estimate all associated parameters, but an individual analysis with linear regression models with random intercept has been made.³⁸ Other studies using ESM in a population between 19 to 40 patients have shown that clinically relevant differences could be detected using an alpha of 0.05.^{1,39-41} However, epidemiologic literature suggest that as a rule-of-thumb, a sample of at least N = 50 is required to evaluate construct validity^{42,43} and to recognize a factor pattern.⁴⁴ Therefore, we need to include at least 50 participants.

Empirical studies using ESM showed that about 5% to 23.2% of the patients did not comply (defined as completing the ESM questionnaire in less than 50% of the beeps).^{1,27,38-41} Taking into account a conservative non-valid ESM data rate of 23%, a sample size of 66 patients is needed to obtain 50 ESM questionnaires that can be used for the analysis.

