6.1 Primary study parameter

Data used for analysis will comprise patient-reported scores from ESM, paper SR-BDs and single-time paper symptom questionnaires. The PROM will be psychometrically evaluated with regard to validity and reliability. These parameters will characterize the ESM measure and allow insight into the potential role of this method in clinical practice. Validity and reliability will be assessed according to following components ^{29,62,63}:

- Content validity reflects the extent to which the instrument as a whole measures all the relevant aspects that are indicative to the specific condition and population. This can be determined by taking into account evidence from qualitative studies, performing cognitive interviews to evaluate patients' understanding with the instrument and by taking into account experts' opinions ^{62,63}. In this study, content validity is assured by basing ESM items on theoretical constructs from the literature as well as by performing patient focus groups and expert meetings.
- Concurrent validity reflects the correlation between a new test and an existing test that purport to measure the same construct. ESM scores will be correlated with scores of so-called 'concurrent' instruments. In the present study, ESM measures will be compared to scores obtained from SR-BDs and symptom questionnaires. Since ESM data have a hierarchical structure, with repeated measurements (level 1) nested within subjects (level 2), these analyses will be performed using linear mixed-effects models, including a random intercept and an autoregressive (AR1) covariate structure. ^{62,63}.
- To quantify the difference of scores between the two methods (ESM and SR-BD), a delta score is calculated. Using the same multilevel analysis, thus adjusting for clustering within patients and for correlations between repeated

measures, we will test whether this delta score is different from 0. In like manner, the differences between SR-BD scores and ESM maximum scores of the day will be tested.

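### The diary-on-ESM association models allow only a random intercept, so the slope's standard error and p-value are valid only if every patient has the same slope, which the plan neither states nor checks

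*Combined protocol and SAP*

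**What the plan says.** Section 6, Part I, specifies linear mixed-effects models "with a random intercept to account for clustering of measurements within patients", together with an AR(1) structure over time. On the outcome it says: "Currently the SR-BD can be seen as the standard method and will therefore be used as dependent variable in the analysis". On the other side of the equation, "ESM day-mean scores of individual symptoms will be used as predictor". Section 6.1 repeats the structure for concurrent validity: "linear mixed-effects models, including a random intercept and an autoregressive (AR1) covariate structure".

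Neither section mentions a random slope, a robust standard error or a check of whether the slope is common to all patients. Two other places come near the subject:

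- Section 6 looks for predictors of the SR-BD minus ESM delta score: "To investigate if certain patient characteristics lead to a different retrospective perception of urgency".
- Section 3.4 says of one cited ESM study that "random slopes could not be included in the multilevel regression analysis because of the sample size being too small". No decision for the present study follows.

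The paired data are thin: the diary covers the last three of the seven ESM days (section 4.2), and section 3.4 aims for 50 patients with usable ESM data. Section 1 says the significance of each correlation coefficient will be checked, and section 6.1 sets alpha at 0.05.

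**The concern.** A random intercept absorbs differences in level: one patient may score the diary higher than another at the same ESM value. It does not absorb differences in slope. The ESM day-mean enters uncentred and varies both between and within patients. A patient whose slope departs from the average therefore leaves residuals that are correlated and grow with the distance of the ESM score from its mean. Neither the random intercept nor AR(1) has that shape. The model then treats the common slope as more precisely known than it is.

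At stake are the standard error, any confidence interval and the p-value of the Part I association, and of the same model reused for concurrent validity.

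**Working it through.** **1. The plan's own figure.** Section 3.4 recruits 66 to keep 50. 50 / (1 − 0.23) = 64.9, so 65; with the upper cited rate, 50 / (1 − 0.232) = 65.1, so 66. The figure is reproduced, and n = 50 with three paired days is the design to examine. The documents state no slope SD, standard error or coverage that could be reproduced.

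**2. Mechanism.** Suppose, for patient i on day j,

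Y_ij = α + a_i + (β + s_i)·X_ij + e_ij,

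with Y the diary day-mean, X the ESM day-mean centred at its overall mean, and s_i the patient's departure from the mean slope, with SD σ_s. The covariance of patient i's residuals is τ²J + σ²R + σ_s²·x_i x_iᵀ, where J is a matrix of ones, R the AR(1) correlation matrix and x_i the patient's vector of X values. The planned model has only the first two terms. Its standard error is right at σ_s = 0 and too small otherwise.

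**3. Simulation.** From the documents: 50 patients, three days, random intercept plus AR(1), alpha 0.05 (taken as two-sided). Assumed, because the documents give none of these: mean slope 0.6, ESM SD 1.5 between and 1.0 within patients, random-intercept SD 1.2, residual SD 1.0, AR(1) correlation 0.3. The main setting used REML fits and 1,500 runs per slope SD. Other settings changed the within-patient ESM SD (0.5, 1.5), the residual SD (1.5), the number of patients (66) and the centring of the random slope. The range column also includes separate, smaller sets of runs.

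| Slope SD | Coverage, main setting | Range over three-day settings | Model SE / true SD, main setting |
|---|---|---|---|
| 0 | 95.9% | 94 to 96% | 1.00 |
| 0.1 | 95.3% | 94 to 96% | 0.98 |
| 0.2 | 93.1% | 91 to 94% | 0.92 |
| 0.3 | 89.8% | 86 to 93% | 0.84 |
| 0.4 | 85.9% | 82 to 90% | 0.77 |

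The low end of the last three ranges comes from within-patient ESM SD 1.5 (90.7, 85.7 and 81.8%).

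**4. False positives.** Subtracting a fixed multiple of X from Y leaves the fitted covariance unchanged, so the rejection rate for a zero average slope equals 100% minus coverage. At slope SD 0.3 this gives 100 − 89.8 = 10.2% in the main setting, and from 100 − 92.8 = 7.2% to 100 − 85.7 = 14.3% over all settings. A separate direct simulation (500 runs) gave 12.8%.

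**5. Remedies, same design (400 runs, Monte Carlo error about 1 to 1.5 points).**

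| Slope SD | Planned model | Planned model, simple cluster-robust SE, t(49) | Random slope added, t(49) |
|---|---|---|---|
| 0 | 94.3% | 93.5% | 96.0% |
| 0.2 | 91.5% | 93.8% | 95.0% |
| 0.3 | 89.8% | 93.3% | 95.5% |
| 0.4 | 88.3% | 93.5% | 96.3% |

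Small-sample-corrected robust standard errors held about 94% in a further run.

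**6. Delta score.** An analysis of patient-mean differences on the same simulated data covered 96 to 97% at every slope SD. This is a simpler analysis than the planned mixed model, but neither contains an ESM slope.

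**The case against.** The strongest objection is that nothing in the documents shows that the slope varies. A reader might infer that the plan itself expects it, and three places tempt that reading. None supports it:

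- The subject-specific patterns in the test-retest hypothesis (section 1) concern agreement of ESM scores between two half-weeks, not the relation of diary to ESM.
- The delta-score predictors in section 6 may reflect pure level shifts, which a random intercept absorbs.
- Section 3.4 describes a limitation of another study.

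This part of the objection stands. What remains is that slope variation is possible: the introduction says recall depends on a person's surroundings and mental state, and the diary is completed after voids while ESM beeps are random. Diary peak reporting, which section 1 expects, does not by itself produce the larger losses. When the weight on the peak was allowed to differ by patient, coverage was about 93% with model-based and robust standard errors alike.

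A second objection is that conclusions would rarely change. The plan announces no interval for this slope and judges validity mainly by the size of correlations (0.4 to 0.8). At slope SD 0.3 and mean slope 0.6, the mean model SE was 0.074 and the robust SE 0.085, against a true SD of 0.088; the zero-slope test rejected in 100% of runs with either. At mean slope 0.4 it rejected in 99.2% and 99.0%. This stands for a strong association such as urgency against urgency. It is weaker for individual symptoms that may be only loosely related, where the p-value carries the message.

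A third objection is that robust standard errors repair only part of the loss. In zero-average-slope runs they still rejected in 8.6% at slope SD 0.2 and 0.3. This too stands, and is why the remedy needs a small-sample correction and should admit a random slope.

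**Conclusion.** The point holds in conditional form. The planned standard error and p-value for the diary-on-ESM slope rely on a common slope that the plan neither states nor checks. Any particular coverage figure belongs to assumed variance components and is not a property of the plan. A reader might take a fixed undercoverage, for example about 90%, as established; the documents do not support that. On the assumptions above there is practically no loss up to slope SD 0.1, a small one at 0.2, and a material one from about 0.3.

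The scope is narrow: one coefficient in the Part I association and its reuse in section 6.1. The delta-score comparisons are not affected in this way. The point is a modest, inexpensive improvement. It does not show that Part I will reach a wrong conclusion.

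**What to change.** In sections 6 and 6.1, choose one of the following in advance:

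- keep the random-intercept and AR(1) model, but take the standard error, confidence interval and p-value of the ESM slope from a patient-clustered robust covariance with a small-sample correction and a t reference; or
- add a random slope for the ESM day-mean, with that robust standard error as the prespecified fallback if the model does not converge.

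In either case, report the estimated between-patient SD of the slope where it can be estimated. With only three diary days per patient it may be imprecise.

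Cost: a sentence or two in the plan, somewhat more analysis, and a check that the named software offers the chosen method. No data or visits are added, and the robust option leaves the point estimate unchanged. If slopes do not vary, the t reference alone widens the interval by about 2.01 / 1.96 = 1.03. If they do, the true SD over the model SE in the main setting gives the widening: 0.0883 / 0.0742 = 1.19 at slope SD 0.3 and 0.1004 / 0.0771 = 1.30 at 0.4, so roughly 20 to 30%.

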Main study endpoints: The main study outcome comprehends the psychometric properties of the PROM for symptom assessment of OAB symptoms. Secondary outcomes are increase in ESM score for OAB symptoms and environmental and psychosocial factors (*e.g.* as measured by the PROM) from one time point (t-1) to the next (t).

Burden, risks and benefits: The burden that is associated with participation in this study comprises completing the PROM questionnaire several times a day, which interrupts daily life due to its random character. Furthermore, the burden is limited to completing a SR-BD and other symptom questionnaires. Most importantly, participating does not bring along

important health related risks. However, awareness could trigger symptoms and therefore be considered as a burden. Nevertheless, for the patients it could be beneficial too to know what triggers complaints, to cope better with their disease.

INTRODUCTION AND RATIONALE

The overactive bladder syndrome (OAB) is defined by the International Continence Society (ICS) as a symptom complex of urgency, usually with frequency and nocturia (awakening at night to void), with (OAB wet) or without (OAB dry) urinary urgency incontinence. Urgency is the complaint of a sudden compelling desire to pass urine, which is difficult to defer⁵. OAB is clinically diagnosed using the ICS criteria of \geq 8 micturitions and at least 1 urgency episode per 24 hours.

It is estimated that approximately 16-17% of the adult population of the Western world is affected by OAB ^{6,7}. The incidence of OAB, both wet and dry increases by age ⁸⁻¹⁰, and because of the worldwide ageing of the population, the number of adults affected by urinary urgency incontinence (UUI) would increase ¹¹. The health care costs of OAB are high ¹², and work productivity can be significantly impacted as well ¹³. In addition, OAB can be associated with comorbidity and increased mortality^{14,15}. Furthermore, OAB with and without incontinence has been associated with significantly lower quality of life scores compared to matched controls without voiding complaints⁸. It is of particular interest that OAB does not only affect the patients, but also has an impact on family members ¹⁰.

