4.1.1 Part I Comparison of the ESM vs. SR-BDs

Main study parameter/endpoint

- Urgency scores as measured by two self-report measures:
 - The ESM tool (*i.e.* momentary measurement)
 - The sensation-related bladder diary (*i.e.* retrospective measurement with a recall period of several minutes)

Secondary study parameters/endpoints (if applicable)

- Symptom scores (other than urgency) as measured using the ESM tool:
 - Micturition habits, *i.e.* number of micturitions each day and the force of the urinary stream using the Visual Prostate Symptom Score (VPSS)
- Symptom scores (other than urgency) as measured using the single-time retrospective questionnaires:
 - Urological symptoms:
 - Female participants: OABq, ICIQ-FLUTS, 3IQ
 - Male participants: OABq, ICIQ-MLUTS, 3 IQ, IPSS, IIEF-5

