4.2 Study procedures

Participants will accomplish the Experience Sampling Method for seven consecutive days during their regular daily life. Previous ESM validation studies validated for the use of the ESM for seven days too.⁴³

During the last three consecutive days of the ESM, patients will also keep a SR-BD following the standard of care. A 7-day voiding diary is a reliable and valid method for documenting the change in symptoms of overactive bladder in men and women with predominantly urge incontinence. However, 3-day voiding diaries are as accurate as the 7-day diary, but patient burden is reduced. Therefore, a 3-day sensation-related bladder diary is used in the standard of care of the department of Urology of MUMC+, Zuyderland Heerlen/Sittard and University Hospital Antwerp.^{46,47} Furthermore, during the first four days of the study, ESM outcomes are not influenced by outcomes reported with the sensation-related bladder diaries. This is in alignment with previous studies.^{4,43}

On the last day of the study period, participants will fill out the several retrospective symptom questionnaires.

To accomplish the ESM, they need to carry their own smartphone or (in case they do not have one) another digital device, which will be lent to them for this period. On the smartphone or digital device an application, specifically developed for this project, will be downloaded. This application will run the PROM as follows.

The concerning device will send out an auditory signal 10 times a day at random moments between 07:00 am and 22:00 pm. During 10 minutes following the signal participants can complete a questionnaire, *i.e.* the developed PROM, on the device (see F1. 'ESM_Vragenlijst_Versie 1.0 (11.08.2017)'). After these 10 minutes the questionnaire will not be available until the next beep and is considered missing data. Therefore, subjects are instructed to complete as many questionnaires as possible each day, as soon as possible following each beep, but to pass over questionnaires when completing is impossible. For example, subjects should not fill out questions when driving a car. The questions will be identical between the different moments during the day.

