4.2.2 Tool development

To apply ESM as a symptom assessment method in this study, an application suitable for smartphones has been developed. This application runs the previously selected set of items, as described in section 5.2.1.1. 'PROM development'.

The application can be downloaded freely on the personal smartphone of each participating subject. Once the application is downloaded and activated, it will work both online and offline to ensure that no assessments will be missed when not connected to the Internet. In online situations the answers will be directly and automatically sent to the general database; when offline the answers will be temporary stored at the smartphone and will be sent to the database as soon as an Internet connection is available. Encryption of data to assure on patient's privacy is described in detail in section 9.1 'Handling and storage of data and documents'.

Questions in the application will be designed in a hierarchical order, *i.e.* if the patient has no symptoms at that particular moment, there is no rationale for assessing triggers and therefore these questions will be automatically set to a default of "no" or "none". Further, if patients find an auditory signal

disturbing during their daily activities, they will be able to choose a vibration signal instead.

- 4.2.3 Retrospective symptom assessment conventional questionnaires Apart from ESM, participants will be instructed to complete a SR-BD during last 3 consecutive days of filling out the ESM (see 'F2. ESM_sensationrelated bladder diary_Versie 1.0 (11.08.2017)'). The SR-BD has to be filled out after each micturition. This is a voiding diary where people fill out at what time they had to void, how high the voided volume was and how high the urgency and perception of bladder fullness was what they experienced. Furthermore they have to fill out if and how much urine loss they had. Furthermore, participants will be instructed to complete additional (singletime) retrospective questionnaires, at the end of the test period of 7 days:
 - Baseline questionnaire for demographic characteristics (see F1.
 'ESM_Algemene Vragenlijst_Versie 1.0 (11.08.2017)').

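### Predictors of the diary-minus-ESM delta cannot be read as predictors of retrospective perception of urgency, because the diary samples voids and ESM samples random moments; section 6.2 also defines the delta differently from section 6

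*Combined protocol and SAP*

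**What the plan says.** **Diary (SR-BD).** Section 4.2.3: "The SR-BD has to be filled out after each micturition". The same section says that it records the degree of urge at each void. Section 4.1.1 calls it a "retrospective measurement with a recall period of several minutes". It is kept on the last three of the seven ESM days (section 4.2).

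**ESM.** Section 4.1.1 describes it as momentary. Under section 4.2 the device signals "10 times a day at random moments between 07:00 am and 22:00 pm".

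**Delta.** Section 6, Part I gives the purpose as "To quantify the difference of scores between the two methods" and the definition as "ESM data will be subtracted from corresponding day-mean SR-BD scores, resulting in a delta score". Section 6.1 adds that "we will test whether this delta score is different from 0". Both sections also compare the diary with the ESM maximum of the day.

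**Predictors.** Section 6 tests gender, age, comorbid panic disorder and HADS as predictors of a larger delta, with the aim "To investigate if certain patient characteristics lead to a different retrospective perception of urgency". Section 6.2 repeats this analysis, but there the diary component is described as an end-of-day score.

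**Expectations.** Section 1, Part I expects mean urgency to be lower on ESM than on the diary, and expects the diary to reflect the daily peak rather than the day's average.

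**The concern.** One instrument is triggered by an event, the void. The other is triggered by the clock. No text in the documents pairs beeps with voids, adjusts for time since or until a void, or cautions that the two sample different moments. The introduction says that "Urgency is the complaint of a sudden compelling desire to pass urine", so equal urgency at and between voids cannot be taken for granted.

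The delta then has two components that the planned analysis cannot separate: a reporting difference, and the true gap between at-void and time-sampled urgency. The predictor analysis attributes its result to the first alone. If followed as written, the report could say that anxious patients, or one sex, perceive urgency differently in retrospect when the data may show only that they have stronger urgency at voids.

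Separately, sections 6 and 6.2 give two definitions of the same analysis variable.

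**Working it through.** **No figure of the plan's own to reproduce.** The documents state no expected delta, standard deviation or power for this analysis. What follows shows only what the sampling difference can do when reporting is perfect.

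**Inputs from the documents.** 10 beeps per day in a 15-hour window (section 4.2); 3 days with both instruments (section 4.2); 50 evaluable patients (section 3.4); alpha 0.05 (section 6.1).

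**Assumptions, not in the documents.** Both items on 0-10 (section 6.1 implies 11 points for ESM; the diary scale is not given); at-void mean 6; SD 1.2 between patients and 1.2 between voids; 8 voids in the window; 70% of beeps completed; zero recall error.

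**Step 1: day-mean delta.** Let U be urgency at the void and f the elapsed fraction of the interval between voids.
- Flat profile: delta = 0.
- Proportional rise, U × f^k: the time average is U/(k+1), so delta = U·k/(k+1). With U = 6: k = 0.25 gives 6 × 0.25/1.25 = 1.2; k = 0.5 gives 6 × 0.5/1.5 = 2.0; k = 1 gives 6 × 1/2 = 3.0; k = 2 gives 6 × 2/3 = 4.0.
- Additive linear rise of a points: delta = a/2, so 1.0 for a = 2 and 2.0 for a = 4.
- Rise only in the last 10 or 5 minutes, from 30% of U: 4.0 or 4.1 by simulation.

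In simulated studies, a t-test of patient-mean deltas against 0 rejects in 4% under the flat profile and in 100% under every rising profile.

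**Step 2: dependence on severity.** Under a proportional rise, delta increases by k/(k+1) per point of at-void severity: 0.20, 0.33, 0.50 and 0.67 for the four values of k. Under an additive rise a/2 does not contain U, so the slope is 0.

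**Step 3: predictor test with no recall difference.** Patient-mean delta regressed on a characteristic that has an assumed correlation with at-void severity; share of simulated studies with p < 0.05:

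| Profile | Correlation 0.3 | Correlation 0.5 |
|---|---|---|
| Proportional, k = 0.25 to 2 | 18-42% | 39-91% |
| Additive or flat | 3-7% | 3-7% |

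A second set of assumptions (10 voids, more spread in severity, k = 2, starting level 0.5) gives 55% and 95%, and 4% when the correlation is 0. The rates depend heavily on the inputs.

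**Step 4: diary mean minus ESM maximum.** Flat -1.45; k = 0.5, -0.18; k = 1, 0.38; k = 2, 1.15. At k = 1 it is 0.80 with 50% of beeps completed and 0.11 with 90%. These values assume ESM without measurement noise. With 1 point of noise the flat value falls to about -2 and the k = 1 value to about 0.1. The sign follows the assumed profile, and the size moves with completion and noise.

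**Step 5: the two definitions.** Section 6 uses the day-mean of the diary. Section 4.2.3 has an entry after each void, from which a day-mean can be formed. Section 6.2 uses an end-of-day score, which a diary completed at each void does not produce.

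**The case against.** The strongest reply is that the plan asks little of the delta. Sections 6 and 6.1 say only that it quantifies a difference between methods, and it does that. **This stands.** A reader might infer that the delta itself, or the test of it against 0, is invalid; the documents do not support that.

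A reader might also infer that the plan takes a lower ESM mean as proof of greater accuracy, or the maximum contrast as proof of distorted recall. It does neither. In section 1 the accuracy hypothesis is followed by the correlation criteria, which this point leaves alone. The lower mean is a separate expectation, and the peak hypothesis names no recall mechanism; it is compatible with sampling at voids.

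The plan also calls the diary retrospective by definition (section 4.1.1) and explains the delta as a difference in urgency reporting. That softens the predictor aim but does not cure it: the stated purpose is still to learn whether characteristics change retrospective perception, with a recall period that the plan puts at minutes.

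The ESM and diary forms are not in the documents. ESM also collects micturition counts and there is a separate morning questionnaire, so some ESM content concerns voids. The label momentary suggests that the urgency item does not, but its wording and reference period cannot be checked. **This stands as a limit on confidence.**

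Finally, all the magnitudes are assumed. **This stands too**, and it is why no expected bias is claimed.

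**Conclusion.** The point holds for the interpretation of the predictor analysis in sections 6 and 6.2, and for the conflicting delta definition in section 6.2. The direction rests on one condition: urgency is higher at voids than on average between them. A spurious predictor needs two more: the gap scales with severity, and the characteristic is related to severity. Under a flat profile or an additive rise the predictor artefact does not arise, so it would be wrong to conclude that the predictor results will be spurious. The documents do not say which case applies, and for that reason a predictor result cannot be given a recall meaning either way.

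Size: unknown from the documents; 0 to about 4 points on an assumed 0-10 scale for the day-mean delta. The conflict of definitions rests on the text alone and needs no assumption. The point should be fixed, but it concerns wording and interpretation, not the main comparison of methods.

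**What to change.** 1. **Sections 6 and 6.2.** Restate the aim, for example: to investigate which patient characteristics are associated with the difference between at-void (SR-BD) and time-sampled (ESM) urgency. Do not interpret the result as retrospective perception.
2. **Section 6.2.** Replace the end-of-day diary score with the day-mean SR-BD score of section 6, so that there is one delta.
3. **Sections 6 and 6.1.** State that neither a lower ESM mean nor a diary mean close to the ESM maximum is by itself evidence of recall distortion. Report completed beeps per day beside the maximum contrast.

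Limiting diary voids to 07:00-22:00 is suited to a sensitivity analysis only. It leaves the void-versus-random-moment mismatch in place and drops night voids, although the introduction includes nocturia in the description of OAB. As an illustration of what it could change, if 2 of 10 voids were at night and differed by 2 points from the rest, the diary day-mean would shift by 2/10 × 2 = 0.4.

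Cost: wording and one descriptive summary, with no new data and no extra burden on patients. The downside is that the plan gives up a recall conclusion, but its design cannot support that conclusion.
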